1.3 Design and methodology

1.3.1 Research design and General Methodological Approach

This study will be designed as a randomized, controlled trial to compare pain and anxiety levels before, during, and after in-clinic abortion in patients with and without a support person in the abortion procedure room. Each procedure day will be randomized into "support person day" ("intervention group") or "non-support person day" ("control group"). This randomization process was chosen as the most effective way to randomize without compromising patient care and study validity. Limitations to the physical space of the health center prevent patient randomization because there is no way to avoid patients knowing which arm of the study they are in: the intervention arm or the control arm.

Randomization will occur at the beginning of each procedure day by a research assistant who will pull from an opaque envelope that contains ten slips of paper, five will be marked with 'A' and the other five marked with 'B'. The half marked 'A' will indicate the procedure day will be assigned as an "intervention" day, and the other half marked 'B' will indicate the day will be assigned as a "control" day. After all ten slips of paper are pulled and ten of the procedure days have been randomized, the research assistant will replace the ten slips of paper and begin the same randomization process until the designated number of participants have been enrolled. The research assistant will initiate enrollment of patients in the study after they have consented for the abortion procedure.

All patients who present at PPSWCF's Tampa Health Center for a dilation and curettage (D&C), whether for elective pregnancy termination or management of early pregnancy complications and who are proficient enough in English to consent and understand the study procedures are eligible for participation and enrollment. Support people will be eligible for participation and enrollment if they are 18 years of age or older, are privately selected by the patient to be their support person, and who are proficient enough in English to consent and understand the study procedures. Support people for minors will be privately selected by the patient in conjunction with their parent/guardian consent.

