1.3.2 Sample Size

A total of 400 subjects will be enrolled in this study; 200 participants will enroll in the control arm and 200 will enroll in the intervention arm. Within these two arms, 100 subjects will be "patients" and "support persons." "Patients" are defined as people who will receive an in-clinic abortion on the day of their participation. "Support persons" are the individuals whom the patient chooses to accompany them during the in-clinic abortion procedure. Support persons will only actually accompany patients in the in-clinic procedure room if they are randomized to the

intervention arm of this study. Health care providers will also be invited to participate in this research study—and enrollment numbers will depend upon the amount of unduplicated staff who will perform or assist with the D&C procedure on days when enrollment will occur. "Health care providers" include the physician performing the abortion and nurses assisting the physician within the abortion procedure room.

Prior studies indicate a 20mm difference in VAS is clinically significant and that the common standard deviation for VAS scores is 23 mm [8]. Based on these assumptions, a sample size of 28 with 14 women in each arm will have 90% power to detect at least a 20mm difference between the change in pain score from baseline, to during the procedure, to after the procedure between the two groups, using a Student's t-test evaluated at the 2-sided 0.05 significance level.

We have chosen a larger sample size to also provide a representative sample of our patient population for our secondary aims of patient and support person satisfaction as well as nurse and physician satisfaction. This sample size was calculated based on the total number of in-clinic abortion patients seen in the Tampa Health Center in 2015 with a Confidence Level of 95% and a Confidence interval of 10.

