1.3.11 Data Analysis

Analysis will be performed using Qualtrics statistical software. Analyses will be performed on all control and experimental group data. The control group is defined as the standard care without presence of support person, whereas the intervention group is all those receiving standard care with the presence of a support person in the procedure room. Demographic, behavioral, and clinical characteristics will be compared between the two arms using frequency tests, Student's ttest, chi-squared tests, and two-way ANOVA, where appropriate. The change in pain score, as assessed by VAS, from baseline to recovery room will be compared within each group using paired Student's t-test if the data are normally distributed or Wilcoxon signed-rank test if the data do not follow a Gaussian distribution. Similarly, the difference in the change in VAS scores between the

study arms will be compared using Student's t- or Mann-Whitney U tests, where appropriate. Questionnaire answers will be compared between both arms of the study using chi-squared statistical analysis. Statistical analysis will be performed by both the Principal Investigator and statistician.

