1.3.12 Study Limitations

Potential weaknesses in the internal validity of this study are addressed through the study design of a randomized controlled trial. Through randomization, the two study groups should theoretically have similar subject characteristics. One potential weakness is that blinding cannot occur. Also, patients in the control group may be dissatisfied and more anxious at baseline due to knowing that they may not have their desired support person in the procedure room.

One limitation in this study is the potential variation among different providers during inclinic abortion; however, all providers will follow the same set standards for the in-clinic abortion procedures. This, combined with the fact that there are only a small number of rotating providers should decrease this potential limitation.

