4.4 VISUAL ANALOG SCALE (VAS)

For these questions we are going to ask you to make an X on a line. For example, let's say you are asked how much you like Oreo cookies:

How much do you like Oreo cookies? (Make an X on the line)

very very little much

Answer the question by making an "X" on the line according to how much you like or dislike Oreo cookies. If you liked Oreo cookies a lot, then you might make an "X" on the line like so:

very / very little / much

If you liked Oreo cookies more than life itself(!), then you might make an "X" on the line like so:

very Very little Very

If you hated Oreo cookies, then you might make an "X" like so:

very very little much

If you thought Oreo cookies were just "OK," then you might make an "X" like so:

very Very little much

The idea is that if you like Oreo cookies, you make an "X" on the line closer to the phrase "very much." The closer you make the "X," the more you are saying you like Oreo cookies. If you don't like Oreo cookies, you make an "X" on the line closer to the phrase "very little." The closer you make the "X," the more you are saying you don't like Oreo cookies.

Please mark an X on the line to indicate your response to the following questions.

1. How much pain do you think you will have during procedure?	
no	worst pain
pain	in my life
ACTUAL TIME OF ASSESSMENT::	
2. How much pain you are having now (immediately at the end oprocedure)?	of the abortion
no	worst pain
pain	in my life
ACTUAL TIME OF ASSESSMENT::	
3. How much pain you are having now (in the post-abortion recent	overy room)? worst pain
	worst pain
pain	in my life
ACTUAL TIME OF ASSESSMENT:	

4.5 POST-PROCEDURE QUESTIONNAIRE FOR SUPPORT PERSON- INTERVENTIONPlease circle your answers below:

1) I had a clear understanding of my role as a support person during the procedure.
Definitely yes
Probably yes
Neutral
Probably not
Definitely not
2) I feel I provided effective support to the patient in the procedure room.
Definitely yes
Probably yes
Neutral
Probably not
Definitely not
3) I feel that the patient was comforted by my presence in the room. Definitely yes
Probably yes
Neutral
Probably not
Definitely not
4) I was comfortable in the procedure room.
Definitely yes
Probably yes
Neutral
Probably not
Definitely not
Don't know/no opinion
Last updated: 4/10/2017

5) If you felt uncomfortable in the procedure room, were you uncomfortable due to any of the following: (circle all that apply)

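### Whole procedure days are randomised, but the between-arm tests and the sample size treat patients as independent, so the two-sided 0.05 level is not held if outcomes correlate within a day

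*Protocol*

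**What the plan says.** - **Allocation (1.3.1).** "Each procedure day will be randomized into" a support-person day or a non-support-person day. One slip is drawn at the start of each day, from an envelope holding five of each kind. The reason given is that "Limitations to the physical space of the health center prevent patient randomization".
- **Sample size (1.3.2).** The calculation is for individual women, "using a Student's t-test evaluated at the 2-sided 0.05 significance level", with a 20 mm difference, SD 23 mm and 90% power. Enrolment is then raised, on survey-precision grounds, to 400 subjects in patient and support-person pairs, read here as 100 patients per arm. No number of days, patients per day, ICC or design effect is given.
- **Analysis (1.3.11).** For the change in VAS score, the "study arms will be compared using Student's t- or Mann-Whitney U tests, where appropriate". The survey items filled in by patients, support persons and staff get a patient-level or form-level test as well: "Questionnaire answers will be compared between both arms of the study using chi-squared statistical analysis".
- **Limitations (1.3.12).** "One limitation in this study is the potential variation among different providers during inclinic abortion". Common standards and a small number of rotating providers are expected to reduce this. No analysis is attached to it.
- **Group definition (1.3.11).** The arms are described by what happened in the room: "whereas the intervention group is all those receiving standard care with the presence of a support person in the procedure room".

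**The concern.** All patients on a given day receive the same allocation, so the day is the unit of randomisation and the trial is cluster-randomised. Student's t, Mann-Whitney and Pearson chi-squared tests all take patients as independent. Patients on one day may share a physician, assisting staff and workload. If that makes their outcomes more alike, the true variance of the difference between arms exceeds what these tests assume. P-values are then too small and confidence intervals too narrow. Balancing five days against five in each block of ten does not remove the correlation.

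The tests are named in the protocol itself, so this is a stated analysis that does not fit the stated design, and not a detail left to a later document. At stake is a modest difference in pain or in questionnaire answers being called significant when it reflects which days fell in which arm. The project summary says the results could change standard practice.

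A smaller, related point is that 1.3.1 defines the arms by the day drawn and 1.3.11 by whether a support person was present. The two part company as soon as there is a deviation.

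**Working it through.** **1. The plan's own sample size.** With a 20 mm difference, SD 23 mm, two-sided 0.05 and 90% power:

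n per arm = 2 × 23² × (1.960 + 1.282)² / 20² = 27.8, so 28 per arm.

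Section 1.3.2 gives 28 in total, 14 per arm, which does not reproduce; 14 per arm has about 60% power by the noncentral t. That is a separate error. What matters here is that the formula has no term for days.

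**2. Inputs for the clustering check.**
- From the protocol: 100 patients per arm and SD 23 mm (1.3.2); recruitment from July to September, about 13 weeks (section 5).
- Assumed, because the protocol does not say: 1 to 3 procedure days a week, taken as 14, 26 or 38 days split equally between arms; within-day ICC 0.02, 0.05 or 0.10.

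**3. Formulas.**
- Patients per day m = 200 / days = 14.3, 7.7 or 5.3.
- Design effect DE = 1 + (m − 1) × ICC.
- Actual two-sided error of a nominal 0.05 patient-level test ≈ 2 × [1 − Φ(1.96 / √DE)].
- Example, 26 days and ICC 0.05: DE = 1 + 6.69 × 0.05 = 1.33; 1.96 / √1.33 = 1.70; error ≈ 9.0%.

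**4. Type I error of the planned t-test.** The simulation used 20,000 null trials per cell, with a normal outcome and a random day effect.

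| Days | ICC | DE | Formula | Simulated |
|---|---|---|---|---|
| 14 | 0.02 | 1.27 | 8.2% | 8.5% |
| 14 | 0.05 | 1.66 | 12.9% | 13.2% |
| 14 | 0.10 | 2.33 | 19.9% | 19.9% |
| 26 | 0.02 | 1.13 | 6.6% | 6.6% |
| 26 | 0.05 | 1.33 | 9.0% | 8.6% |
| 26 | 0.10 | 1.67 | 12.9% | 13.4% |
| 38 | 0.02 | 1.09 | 6.0% | 6.2% |
| 38 | 0.05 | 1.21 | 7.5% | 7.5% |
| 38 | 0.10 | 1.43 | 10.1% | 10.4% |

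Over the same cells, Mann-Whitney ran from 6.0% to 18.7%, and chi-squared on an answer with 70% favourable from 5.7% to 14.1%. With ICC = 0 all three were about 5%. A t-test on day means, or on day proportions, stayed at 4.7% to 5.2%. A wider range of 5 to 20 patients a day and ICC 0.01 to 0.10 gives 5.5% to 25% for the t-test.

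**5. Where the false positives fall.** The planned t-test takes the standard error as 23 × √(2/100) = 3.25 mm, so it declares significance from about 1.97 × 3.25 = 6.4 mm. The correct standard error is 23 × √(0.02 × DE), which is 3.39 mm (DE 1.09) to 4.96 mm (DE 2.33).

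**6. Power.** At SD 23 mm, 20 mm is 20 / 4.96 = 4.0 to 20 / 3.39 = 5.9 correct standard errors, and the day-means test has 96% to 100% power. For 10 mm it has 46% to 81%, while the planned t-test appears to have 77% to 85%.

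**The case against.** The strongest reply is that the size of the harm is assumed. The protocol gives no ICC, no days per week and no patients per day. The 20% figure needs the worst corner, 14 days with ICC 0.10. With 26 to 38 days and ICC 0.02 the error is only 6.2% to 6.6%. Section 1.3.12 speaks of potential provider variation and does not say that one provider works a whole day. If several do, part of that variation lies within days. All of this stands, and it is why the claim is conditional and given as a range. It does not make a patient-level test valid for a day-randomised trial.

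Second, the sample size is not shown to be too small. The 200 patients planned are 3.6 times the 56 from step 1 (200 / 56), more than the largest design effect of 2.33. This also stands. For 1.3.2 the request is to document the clustering, not to enlarge the trial.

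Third, SD 23 mm is quoted for VAS scores, while the tested outcome is a change. Applying 23 mm to the change implies a within-patient correlation of 0.5. With zero correlation the SD would be 23 × √2 = 32.5 mm, and day-level power for 20 mm would run from about 75% to 98%. Section 1.3.2 itself applies 23 mm to the change, so the plan's premise is followed here, but the power statement depends on it.

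Finally, the two group definitions coincide if every day runs as drawn, and the procedure date may well be held in the enrolment log. Both are minor points.

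**Conclusion.** The concern holds: the analysis in 1.3.11 is wrong as written for the design in 1.3.1. The mismatch is certain from the text; its numerical effect is not. If outcomes are uncorrelated within days, the tests are sound. With 100 patients per arm, 14 to 38 days and ICC 0.02 to 0.10, all but the first assumed, the planned tests carry a true type I error of about 6% to 20% for VAS change and about 6% to 14% for a typical questionnaire answer.

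Detection of the planned 20 mm difference is largely unaffected if the SD of the change is 23 mm. The inference at risk is for differences well below 20 mm, which a sample of this size will readily call significant. It must be corrected before analysis because it touches the primary pain comparison.

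**What to change.** Keep day-level randomisation and the planned enrolment.

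- **1.3.11, tests.** Compare arms with a method that respects the day: a t-test on day means, or a mixed model with a random day effect and a small-sample correction to the degrees of freedom. Use a clustered equivalent for categorical answers, such as a comparison of day proportions.
- **1.3.11, groups.** Define the arms as in 1.3.1, so that each patient is analysed in the arm drawn for her day.
- **1.3.2.** State the expected number of procedure days, patients per day, and an assumed ICC range with its design effect.
- **Data.** Make sure that the procedure date is on each patient's record. The VAS form in 4.4 asks for "ACTUAL TIME OF ASSESSMENT", and no form shown in section 4 has a date field, though the enrolment log may hold it.

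The cost is protocol wording and, if needed, one date field. On the plan's SD of 23 mm and the assumed day counts and ICCs, no extra patients are needed for 20 mm. The downside is somewhat larger p-values and less power for smaller differences: for 10 mm over 26 days at ICC 0.05, 73% where the planned t-test appears to give 84%.

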1.1.2 Hypotheses and Objectives

Hypotheses:

Social support in the abortion procedure room will decrease perceived pain and anxiety levels and increase satisfaction for the patient.

- 1. Social support in the procedure room influenced the patient's health outcomes in the following areas:
 - 1. Decreased pain
 - 2. Decreased anxiety
 - 3. Increased patient satisfaction
- 2. The social support person will report that they were able to give effective support to the patient.
- 3. The physician and the nurse will find the support person effective in supporting the patient.

Null Hypothesis:

- 1. Social support in the abortion procedure room will not change patient levels of perceived pain, anxiety, or satisfaction.
- 2. The social support person will report they did not give adequate support.
- 3. The health care provider and the surgical assistant will not find the support person effective

in supporting the patient.

Objectives

Primary Aims:

- To assess a change in expected pain level from baseline, immediately after the procedure, and again ten minutes after arrival to the recovery room as determined by a 100mm visual analog scale (VAS) for patients with in-room social support during the procedure as compared to those who do not.
- To assess pre- and post-procedure state anxiety levels as determined by the 20-question State-Trait Anxiety Inventory (STAI) for patients with in-room social support as compared to patients without in-room social support.

Secondary Aims:

- To measure acceptability and effectiveness of having social support in the procedure room as reported by the surgical assistant and healthcare providers as determined by a post-procedure questionnaire.
- To evaluate if support was effectively given to the patient as reported by the support person as determined by a post-procedure questionnaire.

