1.7 Expected outcomes of the study and dissemination of findings

This study aims to evaluate pain and anxiety levels in patients undergoing in-clinic abortion as well as assess provider and support person satisfaction when support person is in procedure room compared to when support person not in the procedure room. If this study demonstrates that having a support person in the room decreases pain and/or anxiety, this may help to support the inclusion of a support person in the procedure room and improve patient experience. In addition, if providers have a good experience, it may help allay provider concerns about having a support person in the room.

The final results will be presented at a national conference and submitted for publication in a peer-reviewed journal.

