- Facility (ex. too cold, too small, uncomfortable chair, etc)
- Staff (ex. instructions, attentiveness, respect, etc.)
- Beliefs (ex. religious ideology, aversion to medical procedures, etc.)
- Other:
- Not applicable
Please provide additional information:
6) Based on my experience today, I would serve as a support person during an abortion procedure again.
Definitely yes
Probably yes
Neutral
Probably not
Definitely not
Don't know/no opinion
10) Do you have any additional comments or concerns about being a support person in the procedure room?

Thank You!

${\bf 4.6~POST\text{-}PROCEDURE~QUESTIONNAIRE~FOR~SUPPORT~PERSON\text{-}~CONTROL}$

Please circle your answers below:

1. I had a clear understanding of what my role as a support person would have been during the procedure.
Definitely yes
Probably yes
Neutral
Probably not
Definitely not
2. I feel I would have provided effective support to the patient in the procedure room.
Definitely yes
Probably yes
Neutral
Probably not
Definitely not
3. I feel that the patient would have been comforted by my presence in the room. Definitely yes
Probably yes
Neutral
Probably not
Definitely not

4. I believe I would be comfortable being in the procedure room during the in-clinic abortion procedure.
Definitely yes
Probably yes
Neutral
Probably not
Definitely not
Don't know/no opinion
5. Do you have any additional comments or concerns about being a support person in the procedure room?
Thank You!

$\begin{tabular}{ll} \textbf{4.7 POST-PROCEDURE QUESTIONNAIRE FOR HEALTH CARE STAFF-INTERVENTION ARM \\ \end{tabular}$

Please circle your answers below:

1.	The presence of the support person in the procedure room was helpful to me.
	Definitely yes
	Probably yes
	Neutral
	Probably not
	Definitely not
2.	The presence of a support person in the procedure room was helpful to the patient.
	Definitely yes
	Probably yes
	Neutral
	Probably not
	Definitely not
3.	I felt uncomfortable with the support person's presence in the procedure room.
	Definitely yes
	Probably yes
	Neutral
	Probably not
	Definitely not
4.	During the patient's procedure, I felt concerned about the following due to the support person's
	presence: (Please circle all that apply)
	Privacy; please specify
	Security; please specify
	Other
	Not applicable
Las	st updated: 4/10/2017

	Ple	ase prov	e additional information:							
				-						
5)	I felt tha	ıt I had t	provide support to the support person in the procedure room.							
	Definit	ely yes								

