4.8 POST-PROCEDURE QUESTIONNAIRE FOR HEALTH CARE STAFF - CONTROL ARM

Please circle your answers below:

Last updated: 4/10/2017

1.	The presence of the support person in the procedure room would have been helpful to me. Definitely yes
	Probably yes
	Neutral
	Probably not
	Definitely not
2.	The presence of a support person in the procedure room would have been helpful to the patient Definitely yes
	Probably yes
	Neutral
	Probably not
	Definitely not
3.	I would have felt uncomfortable with the support person's presence in the procedure room. Definitely yes
	Probably yes
	Neutral
	Probably not
	Definitely not
4	4. During the patient's procedure, I believe I would have concerns in the following areas if the
5	support person was present: (Please circle all that apply)
	Privacy; please specify
	Security; please specify
	Other
	Not applicable
	Please provide additional information:

28

	accompanied by a support person, I feel like I would have had to provide or the support person.
Definitely yes	
Probably yes	
Neutral	
Probably not	
Definitely not	
6. I would like the ac	ecompaniment in the procedure room to become a permanent arrangement
Definitely yes	
Probably yes	
Neutral	
Probably not	
Definitely not	
. MVA:	
YES or	NO
3. Complications:	
YES or	NO
9. Do you have any a procedure room?	additional comments or concerns about having a support person in the

Thank You!

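### Questionnaire answers are to be compared between arms by chi-squared, but 10 of the 16 paired items (9 on a stricter count) ask a different question in each arm

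*Protocol*

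**What the plan says.** Protocol 1.3.11 fixes the analysis of all the forms in one sentence: "Questionnaire answers will be compared between both arms of the study using chi-squared statistical analysis". The sentences on baseline characteristics and on the between-arm VAS comparison leave room to choose a suitable test. This one does not.

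Section 1.7 gives the purpose as a comparison: to "assess provider and support person satisfaction when support person is in procedure room compared to when support person not in the procedure room". Section 1.1.2 puts the corresponding hypotheses in one-arm terms. Hypothesis 2 is "The social support person will report that they were able to give effective support to the patient" and hypothesis 3 is "The physician and the nurse will find the support person effective in supporting the patient".

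The forms differ by arm. For support persons, item 2 on the intervention form (4.5) reads "I feel I provided effective support to the patient in the procedure room", and on the control form (4.6) "I feel I would have provided effective support to the patient in the procedure room". For staff, item 1 on the intervention form (4.7) reads "The presence of the support person in the procedure room was helpful to me", and on the control form (4.8) "The presence of the support person in the procedure room would have been helpful to me".

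On staff forms, section 1.3.8.3 has the physician, the nurse and other staff in the room each complete one after every procedure. Section 1.3.2 counts staff enrolment by distinct persons, 1.3.4 draws on the same staff for both arms, and 1.3.12 describes the providers as few and rotating. Section 1.3.1 randomises whole procedure days in blocks of ten slips, five per arm.

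**The concern.** A chi-squared test between arms has a clear meaning when both arms answer the same question. Here many items ask intervention respondents about an experience and control respondents about an imagined one. Arm and question change together, so a difference cannot be assigned to the support person.

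At stake are the secondary aims on acceptability and effectiveness. Followed as written, the plan yields p-values that readers would naturally take as effects of accompaniment. It also treats every staff form as a separate respondent, although the same people answer repeatedly.

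**Working it through.** **Step 1. Pair the forms.** I counted closed items with a counterpart in both arms and left out the free-text comment.

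| Forms | Paired closed items | Actual against hypothetical | Remaining |
|---|---|---|---|
| Patient, 4.2 and 4.3 | 4 (items 1, 2, 3, and 8 with control item 4) | 1 (item 3) | 3 |
| Support person, 4.5 and 4.6 | 4 (items 1-4) | 4 (3 without item 1) | 0 (1) |
| Staff, 4.7 and 4.8 | 8 (items 1-8) | 5 (items 1-5) | 3 |
| Total | 16 | 10 (9) | 6 (7) |

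10/16 = 62.5%; 9/16 = 56%. Support-person item 1 is borderline: both versions ask about actual understanding, but in the control arm it is of a role not performed. The denominator is a convention. It is 16 + 3 = 19 if the comment question on each pair of forms is counted, and 16 - 2 = 14 if the factual items (MVA, complications) are dropped. The numerator stays at 10 (9).

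**Step 2. What the test would compare.** For one such item, let pI be the distribution of answers to the actual question in the intervention arm, and pC the distribution of answers to the hypothetical question in the control arm. Chi-squared tests pI = pC. The actual question has no answer in the control arm, because no support person was in the room. So pI - pC mixes any effect of presence with the gap between experience and expectation.
- If control respondents predict accurately, pI = pC however helpful the support person was. A null result is then compatible with full support for hypotheses 2 and 3.
- If they are too pessimistic or too optimistic, pI and pC differ even though accompaniment went exactly as hypothesised.

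Neither outcome of the test bears on the hypotheses.

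**Step 3. Against the aim in 1.7.** Of the support-person pairs, 4 of 4 (strictly 3 of 4) are unlike. Of the six staff opinion items (1-6), 5 are unlike. The sixth, on making accompaniment permanent, shows a don't-know option on the intervention form that the control form lacks. The planned comparison of support-person and provider views therefore rests almost wholly on unlike items.

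**Step 4. What remains comparable.** 16 - 10 = 6 items:
- patient items 1 and 2, worded alike;
- staff items 7 and 8, factual;
- staff item 6, subject to its response options;
- patient item 8 against control item 4, where the intervention wording presupposes having been accompanied already.

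**Step 5. Repeated staff forms.** Reading 1.3.2 as 100 patients per arm gives 2 x 100 = 200 procedures. With at least a physician and a nurse per procedure, that is 2 x 200 = 400 or more forms if all staff consent, from a pool the protocol calls small but does not number. Chi-squared counts these as independent respondents. How far its error rate moves depends on the number of staff, the number of days, how much staff differ and how they are spread over days. None of these is stated. In simulations under assumed values, inflation appeared when one person covered a whole day and vanished when staff rotated within days.

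**The case against.** The paired wording looks deliberate, since control respondents cannot report what they did not experience. Comparing experience with expectation can be a fair descriptive question, and a test of unequal answer distributions is not invalid for that purpose. This stands as a reason to collect and show both sets of answers. It does not rescue the rule, because no section states that contrast as an aim and 1.7 states a different one.

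Hypotheses 2 and 3 are phrased as one-arm reports, and nothing in 1.3.11 forbids answering them from the intervention forms. That is right. The data needed are collected, so the protocol does not make these hypotheses unanswerable; the analysis it names simply does not answer them.

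The SAP is not at hand and may handle repeated raters. That has force for the staff-form issue. It has little for the wording issue, where the protocol itself fixes both test and scope.

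A reader might infer that the staff p-values are inflated by a definite amount, or that MVA and complications are double-counted. The documents do not support either. There is no roster, staff number, day count or intraclass correlation from which to derive a figure, and no section says that forms are pooled across roles. A reader might also extend the criticism to pain and anxiety. The wording problem does not reach them, because the VAS and STAI are the same instruments in both arms. Patient satisfaction (patient item 1) is likewise worded identically.

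**Conclusion.** The rule in 1.3.11 is wrong as written for 10 of the 16 paired closed items, or 9 on the stricter count. For these, a between-arm p-value does not measure an effect of the support person. This conclusion rests only on the wording of the forms and needs no numerical assumption.

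The dependence among staff forms is real in principle, but its size is not established and may be negligible, so no type I error figure should be attached to it. Only secondary questionnaire outcomes are affected. The change should be made before analysis, but the point does not threaten the primary aims.

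**What to change.** Replace the sentence in 1.3.11 with text to this effect:

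- Patient item 3, support-person items 1-4 and staff items 1-5 are reported descriptively by arm, labelled as experienced or anticipated, with no between-arm test.
- Hypotheses 2 and 3 are answered from the intervention-arm forms.
- Between-arm tests are kept to like-worded items: patient items 1 and 2, and staff items 7 and 8 with each procedure counted once. Staff item 6 and patient item 8 against control item 4 are added once wording and response options match.
- Those tests allow for the randomised day, for example by a re-randomisation test that redraws day labels within the blocks of ten.
- Staff opinion items are reported descriptively by role. A two-level staff model is more than these secondary items need.

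The cost is revised analysis text, a role recorded for each staff form, fewer p-values and a little extra analysis. The re-randomisation test may have to be run outside Qualtrics; the protocol does not say what that package can fit.
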